7.2.1 Pharmacokinetic and/or pharmacodynamic samples – not applicable

7.2.2 Pharmacogenetic samples

Refer to [Appendix D](#) for collection and storage of pharmacogenetic samples.

7.3 Labeling and shipment of biohazard samples

The PI ensures that samples are labeled and shipped in accordance with the Laboratory Manual and the Biological Substance, Category B Regulations (materials containing or suspected to contain infectious substances that do not meet Category A criteria), see [Appendix C](#) “IATA 6.2 Guidance Document”.

Any samples identified as Infectious Category A materials are not shipped and no further samples will be taken from the patient unless agreed with AstraZeneca and appropriate labeling, shipment, and containment provisions are approved.

7.4 Chain of custody of biological samples

A full chain of custody is maintained for all samples throughout their life cycle.

The PI at each center keeps full traceability of collected biological samples from the patients while in storage at the center until shipment or disposal (where appropriate) and keeps documentation of receipt of arrival.

The sample receiver keeps full traceability of the samples while in storage and during use until used or disposed of or until further shipment and keeps documentation of receipt of arrival.

AstraZeneca or its representative keeps oversight of the entire life cycle through internal procedures, monitoring of study sites, and auditing of external laboratory providers.

Samples retained for further use are registered in the AstraZeneca biobank system during the entire life cycle.

7.5 Withdrawal of informed consent for donated biological samples

If a patient withdraws consent to the use of donated biological samples, the samples will be disposed of/destroyed, and the action documented. If samples are already analyzed, AstraZeneca is not obliged to destroy the results of this research.

As collection of the biological samples is an optional part of the study, then the patient may continue in the study.

The PI:

- Ensures patients' withdrawal of informed consent to the use of donated samples is notified immediately to AstraZeneca or its representative.
- Ensures that biological samples from that patient, if stored at the study site, are immediately identified, disposed of/destroyed, and the action documented.
- Ensures the laboratory(ies) holding the samples is/are informed about the withdrawn consent immediately and that samples are disposed/destroyed, the action documented, and the signed document returned to the study site.
- Ensures that the patient and AstraZeneca or its representatives are informed about the sample disposal.

AstraZeneca or its representatives ensures the central laboratory(ies) holding the samples is/are informed about the withdrawn consent immediately and that samples are disposed of/destroyed and the action documented and returned to the study site.

8. ETHICAL AND REGULATORY REQUIREMENTS

8.1 Ethical conduct of the study

The study will be performed in accordance with ethical principles that have their origin in the Declaration of Helsinki and are consistent with International Conference on Harmonisation (ICH)/Good Clinical Practice (GCP), applicable regulatory requirements, and the AstraZeneca policy on Bioethics and Human Biological Samples.

8.2 Subject data protection

The ICF will incorporate (or, in some cases, be accompanied by a separate document incorporating) wording that complies with relevant data protection and privacy legislation.

AstraZeneca will not provide individual genotype results to patients, any insurance company, any employer, their family members, general physician, or any other third party, unless required to do so by law.

Extra precautions are taken to preserve confidentiality and prevent genetic data being linked to the identity of the patient. In exceptional circumstances, however, certain individuals might see both the genetic data and the personal identifiers of a patient. For example, in the case of a medical emergency, an AstraZeneca Physician or an investigator might know a patient's identity and also have access to his or her genetic data. Also, regulatory authorities may require access to the relevant files, though the patient's medical information and the genetic files would remain physically separate.

8.3 Ethics and regulatory review

An Institutional Review Board (IRB) should approve the final study protocol, including the final version of the ICF and any other written information and/or materials to be provided to the patients. The investigator will ensure the distribution of these documents to the applicable IRB, and to the study site staff.

The opinion of the IRB should be given in writing. The investigator should submit the written approval to AstraZeneca or its representative before enrollment of any patient into the study.

The IRB should approve all advertising used to recruit patients for the study.

AstraZeneca or its representative should approve any modifications to the ICF that are needed to meet local requirements.

If required by local regulations, the protocol should be re-approved by the IRB annually.

Before enrollment of any patient into the study, the final study protocol, including the final version of the ICF, is approved by the national regulatory authority or a notification to the national regulatory authority is done, according to local regulations.

AstraZeneca or its representative will handle the distribution of any of these documents to the national regulatory authorities.

AstraZeneca or its representative will provide Regulatory Authorities, IRBs, and PIs with safety updates/reports according to local requirements, including Suspected Unexpected Serious Adverse Reactions (SUSARs), where relevant.

Each PI is responsible for providing the IRB with reports of any serious and unexpected adverse drug reactions from any other study conducted with the IP. AstraZeneca or its representative will provide this information to the PI so that he/she can meet these reporting requirements.

8.4 Informed consent

The PI(s) at each center will:

- Ensure each patient is given full and adequate oral and written information about the nature, purpose, possible risk, and benefit of the study.
- Ensure each patient is notified that they are free to discontinue from the study at any time.
- Ensure that each patient is given the opportunity to ask questions and allowed time to consider the information provided.
- Ensure each patient provides signed and dated ICF before conducting any procedure specifically for the study.
- Ensure the original, signed ICF(s) is/are stored in the investigator's Study File.
- Ensure a copy of the signed and dated ICF is given to the patient.
- Ensure that any incentives for patients who participate in the study as well as any provisions for patients harmed as a consequence of study participation are described in the ICF that is approved by an IRB.

8.5 Changes to the protocol and informed consent form

Study procedures will not be changed without the mutual agreement of the PI and AstraZeneca.

If there are any substantial changes to the study protocol, then these changes will be documented in a study protocol amendment and where required in a new version of the study protocol (Revised CSP).

The amendment is to be approved by each IRB and if applicable, also the national regulatory authority, before implementation. Local requirements are to be followed for revised protocols.

AstraZeneca will distribute any subsequent amendments and new versions of the protocol to each PI. For distribution to the IRB, see Section 8.3.

If a protocol amendment requires a change to a center's ICF, AstraZeneca and the center's IRB are to approve the revised ICF before the revised form is used.

If local regulations require, any administrative change will be communicated to or approved by each IRB.

8.6 Audits and inspections

Authorized representatives of AstraZeneca, a regulatory authority, or an IRB may perform audits or inspections at the center, including source data verification. The purpose of an audit or inspection is to systematically and independently examine all study-related activities and documents, to determine whether these activities were conducted, and data were recorded, analyzed, and accurately reported according to the protocol, GCP, guidelines of the ICH, and any applicable regulatory requirements. The investigator will contact AstraZeneca immediately if contacted by a regulatory agency about an inspection at the center.

9. STUDY MANAGEMENT BY ASTRAZENECA

9.1 Pre-study activities

Before the first patient is entered into the study, it is necessary for a representative of AstraZeneca to visit the investigational study site to:

- Determine the adequacy of the facilities
- Determine availability of appropriate patients for the study
- Discuss with the investigator(s) (and other personnel involved with the study) their responsibilities with regard to protocol adherence, and the responsibilities of AstraZeneca or its representatives. This will be documented in a CSA between AstraZeneca or its representative and the investigator.

9.2 Training of study site personnel

Before the first patient is entered into the study, an AstraZeneca representative or its representative will review and discuss the requirements of the CSP and related documents with the investigational staff and also train them in any study-specific procedures, the eDiary recording device, and other system(s) utilized.

The PI will ensure that appropriate training relevant to the study is given to all of these staff, and that any new information relevant to the performance of this study is forwarded to the staff involved.

The PI will maintain a record of all individuals involved in the study (medical, nursing, and other staff).

9.3 Monitoring of the study

During the study, an AstraZeneca representative or its representative will have regular contacts with the study site, including visits to:

- Provide information and support to the investigator(s)

- Confirm that facilities remain acceptable
- Confirm that the investigational team is adhering to the protocol, that data are being accurately and timely recorded in the eCRFs, that biological samples are handled in accordance with the Laboratory Manual, and that study drug accountability checks are being performed
- Perform source data verification (a comparison of the data in the eCRFs with the patient's medical records at the hospital or practice, and other records relevant to the study) including verification of informed consent of participating patients. This will require direct access to all original records for each patient (eg, clinic charts)
- Ensure withdrawal of informed consent to the use of the patient's biological samples is reported and biological samples are identified and disposed of/destroyed accordingly, and the action is documented, and reported to the patient.

The AstraZeneca representative or its representative will be available between visits if the investigator(s) or other staff at the center needs information and advice about the study conduct.

9.3.1 Source data

Refer to the CSA for location of the source data.

9.4 Study agreements

The PI at each center should comply with all the terms, conditions, and obligations of the CSA, or equivalent, for this study. In the event of any inconsistency between this CSP and the CSA, the terms of the CSP shall prevail with respect to the conduct of the study and the treatment of patients and in all other respects, not relating to study conduct or treatment of patients, the terms of the CSA shall prevail.

Agreements between AstraZeneca and the PI should be in place before any study-related procedures can take place, or patients are enrolled.

Prior to a patient's enrollment in the study and any study-related procedures are undertaken, the following should be fulfilled:

- Signed CSA between AstraZeneca and the PI/study center
- Signed CSP and other agreements between AstraZeneca and the PI/study center
- Written approval of the study by the IRB
- Signed and dated Financial Disclosure forms.

9.4.1 Archiving of study documents

The investigator follows the principles outlined in the CSA.

9.5 Study timetable and end of study

The end of the study is defined as “the last visit of the last patient undergoing the study.” The end of study definition is for the entire study.

The study is expected to start in 1st Quarter [REDACTED] and to end by 4th Quarter [REDACTED].

The study may be terminated at individual centers if the study procedures are not being performed according to GCP, or if recruitment is slow. AstraZeneca may also terminate the entire study prematurely if concerns for safety arise within this study or in any other study with NKTR-118.

10. DATA MANAGEMENT BY ASTRAZENECA

10.1 Electronic case report form

The eCRF and the protocol are both confidential. The eCRF will be created by the contract research organization (CRO) and programmed into the eDC system. All study sites will need internet access to access the eCRFs and will only have access to data for patients at their own study sites. Data management (DM) and other co-ordinator teams will have access to data at all study sites.

All eCRFs are to be completed by an authorized member of the investigational staff and reviewed and signed by the investigator. All entries, corrections, and alterations are to be made by the responsible investigator or an authorized member of the investigational staff. All eCRFs are to be completed in a manner that ensures accurate interpretation of data.

It is each investigator’s responsibility to ensure that all discontinued orders or changes in the study or other medications entered on the patient’s eCRF correspond to the entries on the patient’s medical records.

The eCRFs for any patient leaving the study should be completed at the time medication is terminated for whatever reason.

The eCRFs must accurately reflect data contained in patient’s records (eg, source documents).

10.2 Data flow

After data are entered into the eCRF by study site, autoqueries that are generated by the eDC system should be addressed by study site. Data queries will be raised for inconsistent, impossible, or missing data. All entries to the study database will be available in an audit trail.

Data entered in the eDC system will be immediately saved to a central database and changes tracked to provide an audit trail. When the PI has signed the eCRF electronically as per eCRF instructions, then the patient's data will be locked.

The data collected through third party sources will be obtained and reconciled against study data.

The data will be validated as defined in the DM Plan. Quality control procedures will be applied to each stage of data handling to ensure that all data are reliable and have been processed correctly.

At the monitoring visit, the Study Monitor must perform the Source Document Verification (SDV) of the required fields on completed forms and if there are no open queries, freeze the form. Data management will run manual consistency checks outside of the eDC system and will raise manual queries for study sites to address; if the form is frozen, DM will unfreeze to allow study sites to amend data. The same process is to be followed by any other groups creating manual queries in the eDC system (eg, for SAE reconciliation). Once all data are entered, SDV complete on required fields, manual queries and electronic data reconciliation complete, and all queries closed, then the casebook can be signed. Once the casebook is signed, DM will then lock the casebook so that no amendments can be made.

10.3 Database lock

When all data have been coded, validated, signed, and locked, a clean file will be declared. Any treatment revealing data may thereafter be added and the final database will be locked.

Once all patient casebooks are locked, the final data transfer can be sent to statistics. A database lock checklist will also be completed by DM and the programmer to confirm all applicable quality control checks were performed.

10.4 Coding

All AEs and medical/surgical histories recorded in the eCRF will be coded using MedDRA. All medications will be classified according to the AstraZeneca Drug Dictionary (AZDD). All coding will be performed by the CRO. The coding will occur outside of the eDC system and will be merged with the clinical datasets sent to statistics.

10.5 Investigator site file

At the beginning of the study, an investigator's study file will be established at the study center. The investigator/institution is responsible for maintaining the study documents as specified in the guideline for ICH GCP (Committee for Proprietary Medicinal Products [CPMP]/ICH/135/95) and as required by the applicable regulatory requirement(s). The investigator/institution must take measures to prevent accidental or premature destruction of these documents.

10.6 SAE reconciliation

The CRO will perform SAE reconciliation between the CRO Clinical Study database and the AstraZeneca Clinical Patient Safety database.

10.7 ECG data

ECG data will be processed by a central laboratory and the results will be sent electronically to AstraZeneca or its representative.

11. EVALUATION AND CALCULATION OF VARIABLES

11.1 Calculation or derivation of safety variable(s)

11.1.1 Adverse events

A treatment-emergent adverse event (TEAE) is defined as any AE that started on or after the first dose of study drug up to the last dose of study drug. An AE already present at the time of the first dose of study drug that worsens in intensity following exposure to study drug or an AE with an unknown/not reported onset date will also be considered as treatment-emergent. Adverse events occurring after the last dose of study drug will also be summarized, which among other purposes, may assess any potential withdrawal-type effects.

Time to onset of an AE (in days) will be calculated as:

$$\text{AE start date} - \text{Date of the first dose of study drug} + 1.$$

Duration of an AE (in days) will be calculated as:

$$\text{AE resolution date} - \text{AE start date} + 1.$$

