6.3.4 Recording of adverse events

Time period for collection of adverse events

All AEs will be collected from the time of signature of informed consent to the follow-up visit (Visit R15), whether or not related to the IP and must be recorded on the eCRF. Unsolicited reports of SAEs will also be collected for 30 days after the last dose of study drug.

Follow-up of unresolved adverse events

Any AEs that are unresolved at the patient's last AE assessment in the study are followed up by the investigator for as long as medically indicated, but without further recording in the eCRF. AstraZeneca or its representative retains the right to request additional information for any patient with ongoing AE(s)/SAE(s) at the end of the study, if judged necessary.

Variables

The following variables will be collect for each AE;

- AE (verbatim)
- The date when the AE started and stopped
- Maximum intensity or intensity or changes in intensity
- Whether the AE is serious or not
- Investigator causality rating against the study drug (yes or no)
- Action taken with regard to IP
- AE caused patient's discontinuation from study (yes or no)
- Outcome.

In addition, the following variables will be collected for SAEs:

- Date AE met criteria for SAE
- Date investigator became aware of SAE
- Seriousness criteria
- Date of hospitalization
- Date of discharge
- Probable cause of death
- Date of death
- Autopsy performed
- Causality assessment in relation to study procedure(s)
- Causality assessment in relation to other medication
- Description of AE (including treatment administered and dechallenge/rechallenge information, if applicable).

Intensity is defined as follows:

- Mild (awareness of sign or symptom, but easily tolerated)

- Moderate (discomfort sufficient to cause interference with normal activities)
- Severe (incapacitating, with inability to perform normal activities).

Other reporting guidance

It is important to distinguish between serious and severe AEs. Severity is a measure of intensity whereas seriousness is defined by the criteria in Section 6.3.3. An AE of severe intensity need not necessarily be considered serious. For example, nausea that persists for several hours may be considered severe nausea, but not an SAE. On the other hand, a stroke that results in only a limited degree of disability may be considered a mild stroke, but would be an SAE.

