6.3.13.2 Persistent or progressive severe abdominal pain

Rare cases of GI perforation associated with the use of other peripheral opioid antagonists in OIC have been reported in a post-marketing setting. Such cases of perforation have been reported to occur shortly after initiation with drug and appear to be more commonly reported in debilitated patients with multiple co-morbidities, particularly co-morbid conditions that might impair the local or global structural integrity of the GI tract (eg, cancer, peptic ulcer, pseudo-obstruction of the colon, etc.; see Section 1.4 and Section 4.2).

While abdominal pain has been reported in association with NKTR-118 use in a Phase II OIC trial, any at-risk patient who reports progressive or persistent severe abdominal pain should be evaluated immediately by the site or otherwise referred for urgent medical assessment. Other associated symptoms with abdominal pain such as fever, malaise, and or mental status changes should also mandate urgent medical evaluation.

In addition, it should be emphasized that a thorough screening abdominal/rectal examination is an important element in identifying pre-treatment findings that might identify a patient who is at high risk for perforation. The investigator should maintain a low threshold for considering abdominal x-rays, further abdominal/rectal examination, or other diagnostic aids based on clinical assessment and patient history.

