12.2.1 Safety analyses

Adverse events will be coded using the MedDRA dictionary. Three sets of AE summaries will be generated: (1) all AEs recorded in the clinical database, (2) all TEAEs (as defined in Section 11.1.1), and (3) AEs occurring after the last dose of study drug.

Number of events and proportions will be tabulated by preferred term and system organ class. An event that occurred 1 or more times on the date of or subsequent to first dose of study drug will contribute 1 observation to the numerator of the proportion. The denominator of the proportion will comprise all patients in the Safety analysis set. Adverse events will also be

summarized by intensity and separately, by causality (as determined by the investigator). Should a patient experience the same preferred term/system organ class within multiple intensity or causality categories, the patient's worst occurrence (most severe/most related) will be retained in the tabulations. Serious AEs and commonly occurring AEs will be summarized in a generally similar manner. Adverse events of special interest may be further summarized and analysis of AEs occurring within specific time periods (e.g. after 3 months, after 6 months, etc.) may be considered.

Adverse events, SAEs, AEs leading to death, and AEs leading to study discontinuation will be tabulated for each treatment group. Descriptive statistics for time to onset and duration of select AEs may be summarized by treatment group. Adverse events that could potentially be indicative of centrally mediated opioid withdrawal, abuse potential, and bowel perforation will be identified prior to database lock and will also be summarized by each treatment group.

The mean daily opioid dose will be summarized for the following intervals: randomization to Month 1, Months 1 to 3, Months 3 to 6, Months 6 to 9, and Months 9 to 12. The mean bisacodyl dose per week will be summarized only for the NKTR-118 treatment group using descriptive statistics for the following intervals: randomization to Month 1, Months 1 to 3, Months 3 to 6, Months 6 to 9, and Months 9 to 12. The observed composite modified Himmelsbach score and change from baseline will be summarized by treatment group at Week 1, Months 1, 3, 6, 9, and 12 using descriptive statistics. The observed score and change from baseline in the NRS pain scores (average in the 7 days prior to the study visit) will be summarized by treatment group for Weeks 1 and 2, Months 1, 2, 3, 6, 9, and 12.

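### Time to AE onset is zero or negative for treatment-emergent AEs that qualify by worsening, and its starting point for rollover patients is not stated (minor)

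*Protocol*

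**What the plan says.** Protocol Section 11.1.1 defines a treatment-emergent AE as one starting between the first and last dose of study drug. It adds two further routes, one of which is "An AE already present at the time of the first dose of study drug that worsens in intensity following exposure to study drug". The same section then fixes one formula for all AEs: "Time to onset of an AE (in days) will be calculated as" the AE start date minus the "Date of the first dose of study drug", plus 1. It makes no exception for AEs that qualify by worsening and does not say which study's first dose is meant.

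Section 6.3.4 lists what is recorded for each AE: "The date when the AE started and stopped", and "Maximum intensity or intensity or changes in intensity". A date of worsening is not listed as a separate item. On the collection window, it says "All AEs will be collected from the time of signature of informed consent".

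Section 12.2.1 says how the variable is used: "Descriptive statistics for time to onset and duration of select AEs may be summarized by treatment group".

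The rollover setting comes from Section 3.1. Patients may enter on the last treatment day of D3820C00005 or of the extension D3820C00007, and the 52-week treatment period of this study starts that day.

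**The concern.** There are two separate problems.

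**Worsened AEs.** The definition and the formula in Section 11.1.1 do not fit together. The definition admits AEs that began before dosing, because the event of interest is the worsening after dosing. The formula then dates them by their beginning. A treatment-emergent AE can thus have an onset before treatment, which is not a meaningful value. Any such values would pull the mean and median onset down in the summaries foreseen in Section 12.2.1.

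**Rollover patients.** Baselines in Sections 11.1.5 to 11.1.12 and 12.2 are tied explicitly to this study or to the previous pivotal study. Section 11.1.3 also separates the two randomizations for the mean opioid dose. The onset formula has no such qualifier. For a patient who took NKTR-118 before and continues on it here, time since first dose in this study is not time since starting NKTR-118. A single summary by treatment group would put first-exposed and continuing patients on one clock without saying so.

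**Working it through.** The plan states no figure to reproduce. The check applies its formula to the dates its own schedule allows.

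**Inputs**
- Onset = AE start date − first-dose date + 1 (Section 11.1.1).
- New patients: consent at S1; S2 is 5 to 14 days after S1 (Section 3.1.1.2); R1 is 14 days after S2, −1 to +3 days (Section 3.1.2.1). Longest interval from consent to R1: 14 + 14 + 3 = 31 days.
- Earlier treatment: 12 or 24 weeks (Section 1.4), ie 12 × 7 = 84 or 24 × 7 = 168 days.

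**Worsened AEs in new patients.** If the AE began *d* days before the first-dose date, onset = −*d* + 1, whenever the worsening occurred.

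| AE start relative to first dose | Onset by the formula |
|---|---|
| same date | 1 |
| 1 day before | 0 |
| 2 days before | −1 |
| 14 days before | −13 |
| 28 days before | −27 |
| 31 days before | −30 |

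For illustration, an AE that began 20 days before the first dose and worsened on Day 10 is given −20 + 1 = −19. Dated by its worsening, it has onset 10. With the date of worsening in the formula, every such AE has onset of at least 1.

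**Rollover anchor.** Take an AE starting on Day 5 of this study, with uninterrupted dosing assumed.

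| Patient | Anchor: this study | Anchor: pivotal study, 12 weeks | Anchor: pivotal study, 24 weeks |
|---|---|---|---|
| NKTR-118 before, NKTR-118 now | 5 | 84 + 5 = 89 | 168 + 5 = 173 |
| Placebo before, NKTR-118 now | 5 | 89 | 173 |

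For time since starting NKTR-118, the pivotal anchor suits the first row and the this-study anchor suits the second. No single unqualified first dose serves both. Section 12.1.1 describes study drug as NKTR-118 25 mg or Usual Care, which makes the this-study reading the natural one, but Section 11.1.1 does not say so.

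**The case against.** The best defence is that little depends on this. The onset summary is something that may be produced, for selected AEs, with no testing. No objective and no sample-size argument rests on it. The date used for a worsened AE is often settled in the SAP, which is not at hand. That limits the importance but does not remove the point: the protocol has itself fixed a formula, and followed exactly it gives impossible values.

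A this-study clock is also a legitimate choice. It matches the comparison of arms as randomized here, and Day 1 is then the same visit in both arms. Nor would a pivotal-study clock simply be better. Rollover patients had to complete the earlier study, so their AEs starting in this study would have onset of at least Day 85 or 169 by construction. The pivotal studies also tested 12.5 mg (Section 3.2); for those patients R1 is the true start of 25 mg. All of this stands, and it is why the this-study anchor should be stated and kept as primary.

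Section 12.2 already foresees AE summaries, where appropriate, by new or rollover status and by the combination of previous and current treatment. This would separate the patients, but it does not name the anchor.

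Three stronger readings are tempting and are not supported:
- *Earlier exposure is lost.* Section 12.2.1 combines current exposure with that from the pivotal studies. Only the onset clock is affected, and only for patients on NKTR-118 both before and after rollover.
- *The onset analysis exists to detect early perforation.* Section 6.3.13.2 does say "Such cases of perforation have been reported to occur shortly after initiation with drug", about other drugs of the class, but as a reason for clinical vigilance. Section 12.2.1 gives no reason for the onset summary.
- *AEs carried over by rollover patients produce large negative onsets.* Sections 3.1.2.1 and 6.2.1 enter AEs ongoing at rollover as medical history. Nothing says that their original start dates feed the formula.

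**Conclusion.** The point holds, at minor severity.

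The firm part is the mismatch within Section 11.1.1. Any AE that began before the first-dose date and qualifies by worsening has an onset of 0 or less, down to about −30 days for a new patient with the longest permitted run-in. This follows from the text and the visit schedule alone. How many AEs are affected, and how far a mean or median would shift, cannot be worked out from the protocol.

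The second part is an omission. The anchor for rollover patients is not stated. The 84 or 168 days missing from the clock rest on the this-study reading, on full 12- or 24-week earlier treatment with NKTR-118, and on continuous dosing across rollover. They do not apply to patients previously on placebo or Usual Care, or now on Usual Care.

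Neither part touches AE incidence, total exposure or any objective of the study. The effect is confined to an optional descriptive summary, which as written could contain impossible values and mix two meanings of onset.

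**What to change.** In Section 11.1.1:

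1. For AEs that are treatment-emergent because they worsened, define onset as date of worsening minus first-dose date plus 1. Section 6.3.4 allows changes in intensity to be recorded; where the date of worsening is not collected, leave the AE out of the onset statistics and report how many were left out.
2. State that the primary anchor for onset is the first dose in this study, for new and rollover patients alike.
3. Where onset is summarized, show first-exposed and continuing NKTR-118 patients separately. For the continuing patients add a supplementary onset from the first NKTR-118 dose in the previous study, distinguish previous 12.5 mg from 25 mg, and note that these patients had to complete the earlier study to be included.

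The cost is a few lines of text and a small amount of extra programming. Section 12.2 already integrates baseline data from the earlier studies and Section 12.2.1 their exposure data. The only new data need would be the date of worsening, if the eCRF does not already hold it, and item 1 covers that case.
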